Febrile neutropenia (ANC < 1.0×10^9 /L, with a single temperature of >38.3 degrees C [101 degrees F] or a sustained temperature of \geq 38 degrees C [100.4 degrees F] for more than one hour)	Mandatory: Interrupt study treatment until resolved, then reduce 1 dose level.
Anaemia	
Grade 1 (Hemoglobin [Hgb] < LLN - 10.0 g/dL; < LLN - 6.2 mmol/L; < LLN - 100 g/L)	Recommendation: Maintain study treatment and dose level.
Grade 2 (Hgb < 10.0 - 8.0 g/dL; < 6.2 - 4.9 mmol/L; < 100 - 80 g/L)	Recommendation: Maintain study treatment and dose level.
Grade 3 (Hgb < 8.0 g/dL; < 4.9 mmol/L; < 80 g/L; transfusion indicated)	Recommendation: Interrupt study treatment until resolved to ≤ grade 2, then:
	If resolved in ≤ 7 days, resume study treatment at the same dose level;
	If resolved in > 7 days, reduce 1 dose level.
Grade 4 (Life-threatening consequences; urgent intervention indicated)	Mandatory: Interrupt study treatment until resolved to ≤ grade 2, then reduce 1 dose level.

Investigations (Renal)	
Serum creatinine	
Grade 1 (> ULN - 1.5 × ULN)	Recommendation: Maintain study treatment and dose level.
Grade 2 (> 1.5 - 3.0 × ULN)	Recommendation: Interrupt study treatment and manage according to institutional practice.
	Upon resolution to ≤ Grade 1, may reintroduce study treatment at the same dose level if clinically indicated.
Grade 3 (> 3.0 - 6.0 × ULN) and Grade 4 (> 6.0 × ULN)	Mandatory: Permanently discontinue study treatment.
Investigations (Hepatic)	
Isolated total Bilirubin elevation	
Grade 1 (> ULN – 1.5 × ULN)	Recommendation: Maintain study treatment and dose level.
Grade 2 (> 1.5 - 3.0 × ULN)	Recommendation: Interrupt study treatment.
	Repeat LFTs ^b within 48-72 hours, then monitor LFTs at least weekly, until resolved to ≤ 1.5 × ULN or to baseline, then:
	• If resolved in ≤ 7 days, resume study treatment at the same dose level;
	If resolved in > 7 days, reduce 1 dose level.
Grade 3 (> 3.0 - 10.0 × ULN)*	Recommendation: Interrupt study treatment.
	Repeat LFTs ^b within 48-72 hours, then monitor LFTs at least weekly, until resolved to ≤ 1.5 × ULN or to baseline. May reintroduce study treatment at 1 lower dose level if clinically indicated.
Grade 4 (> 10.0 × ULN)*	Mandatory: Permanently discontinue study treatment.
	The participant should be monitored at least weekly (including LFTs ^b), or as clinically indicated, until total bilirubin has resolved to ≤ 1.5 × ULN or to baseline.

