If combined elevations of AST or ALT and total bilirubin do not meet the defined thresholds, please follow the instructions for isolated elevation of total bilirubin and isolated elevation of AST/ALT, and take a conservative action based on the degree of the elevations (e.g., permanently discontinue treatment at the situation when omit dose is needed for one parameter and permanently discontinue treatment is required for another parameter). After all elevations resolve to the defined thresholds that allow treatment re-initiation, re-start the treatment either at the same dose or at one dose lower if meeting a criterion for dose reduction

^d "Cholestasis" defined as ALP elevation (> 2.0 × ULN and R value < 2) in participants without bone metastasis or elevation of ALP liver fraction in participants with bone metastasis

Note: The R value is calculated by dividing the ALT by the ALP, using multiples of the ULN for both values. It denotes whether the relative pattern of ALT and/or ALP elevation is due to cholestatic ($R \le 2$), hepatocellular ($R \ge 5$), or mixed (R > 2 and R > 5) liver injury

- * Note: If total bilirubin > 3.0 × ULN is due to the indirect (non-conjugated) component only, and hemolysis as the etiology has been ruled out as per institutional guidelines (e.g., review of peripheral blood smear and haptoglobin determination), then reduce 1 dose level and continue treatment at the discretion of the Investigator.
- **Note: A CT scan or other imaging study to assess the pancreas, liver, and gallbladder must be performed within 1 week of the first occurrence of any ≥ Grade 3 elevation of amylase and/or lipase. If asymptomatic Grade 2 elevations of lipase and/or amylase occur again at the reduced dose, participants will be permanently discontinued from study treatment.
- *** Note: Antidiarrheal medication is recommended at the first sign of abdominal cramping, loose stools, or overt diarrhea

**** Note: JDQ443 has shown CC . The Investigators should recommend the use of precautionary measures against CC . To the participants during treatment with JDQ443 CC .

Table 6-4 Dose reduction steps for JDQ443

Dose reduction*	Starting dose level 0	Dose level – 1	Dose level – 2
JDQ443	200 mg b.i.d.	100 mg b.i.d.	100 mg QD. (once a day)**

^{*}Dose reduction should be based on the worst toxicity demonstrated at the last dose.

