Any clinical event of jaundice (or equivalent term)
• ALT or AST > 3 x ULN accompanied by (general) malaise, fatigue, abdominal pain, nausea, or vomiting, or rash with eosinophilia
Any adverse event potentially indicative of a liver toxicity
ALT or AST > 3 x baseline or > 300 U/L (whichever occurs first)

Table 10-2 Follow-up requirements for liver laboratory triggers - ALT, AST, bilirubin

ALT	TBL	Liver Symptoms	Action
ALT increase without bilirubin increase:			

เพองสเนธ	Cornidential
Amended Protocol Version No.01 (Clean)	
•	

ALT	TBL	Liver Symptoms	Action
If normal at baseline: ALT > 3 x ULN If elevated at baseline: ALT > 2 x baseline or > 300 U/L (whichever occurs first)	Normal For participants with Gilbert's syndrome: No change in baseline TBL	None	· No change to study treatment · Measure ALT, AST, ALP, GGT, TBIL, INR, albumin, CK, and GLDH in 48-72 hours. · Follow-up for symptoms.
If normal at baseline: ALT > 5 x ULN for more than two weeks If elevated at baseline: ALT > 3 x baseline or > 300 U/L (whichever occurs first) for more than two weeks	Normal For participants with Gilbert's syndrome: No change in baseline TBL	None	· Interrupt study treatment · Measure ALT, AST, ALP, GGT, TBIL, INR, albumin, CK, and GLDH in 48-72 hours. · Follow-up for symptoms.
If normal at baseline: ALT > 8 x ULN	Normal	None	Initiate close monitoring and workup for competing etiologies.
ALT increase with bilirub	in increase:		· Study treatment can be
If normal at baseline: ALT > 3 x ULN	TBL > 2 x ULN (or INR > 1.5)	None	restarted only if another etiology is identified and liver enzymes return to
If elevated at baseline: ALT > 2 x baseline or > 300 U/L (whichever occurs first)	For participants with Gilbert's syndrome: Doubling of direct bilirubin		baseline.
If normal at baseline: ALT > 3 x ULN	Normal or elevated	Severe fatigue, nausea, vomiting, right upper	
If elevated at baseline: ALT > 2 x baseline or > 300 U/L (whichever occurs first)		quadrant pain	

Follow-up requirements for liver laboratory triggers - isolated hyperbilirubinemia **Table 10-3**

Criteria	Actions required	Follow-up monitoring
Total Bilirubin (isolated)	7 totalono roquirou	Tonon up monitoring
>1.5 – 3.0 ULN	Maintain treatment Repeat LFTs within 48-72 hours	Monitor LFTs weekly until resolution to ≤ Grade 1 or to baseline

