> 3 - 10 × ULN (in the absence of known Gilbert syndrome)	 Interrupt treatment Repeat LFT within 48-72 hours Hospitalize if clinically appropriate Establish causality Record the AE and contributing factors (e.g. conmeds, med hx, lab) in the appropriate eCRF 	Monitor LFTs weekly until resolution to ≤ Grade 1 or to baseline (ALT, AST, total bilirubin, Alb, PT/INR, ALP and GGT) Test for hemolysis (e.g. reticulocytes, haptoglobin, unconjugated [indirect] bilirubin)
> 10 x ULN	Discontinue the study treatment immediately Hospitalize the participant	ALT, AST, total bilirubin, Alb, PT/INR, ALP and GGT until

Criteria	Actions required	Follow-up monitoring
	Establish causality Record the AE and	resolution (frequency at Investigator discretion)
contributing factors(e.g. conmeds, med hx, lab)in the appropriate eCRF		
Any AE potentially indicative of a liver toxicity	Consider study treatment interruption or discontinuation	Investigator discretion
	Hospitalization if clinically appropriate	
	Establish causality	
	Record the AE and contributing factors(e.g., conmeds, med hx, lab)in the appropriate eCRF	

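### Table 6-3 and the Appendix 5 liver tables give different dosing actions for mild isolated bilirubin and ALT rises, and above 3 x ULN bilirubin where footnote * applies, and no sentence says which table prevails

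*Protocol*

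**What the plan says.** **Bilirubin, Table 6-3 (Protocol 6.5.1).** For an isolated rise above 1.5 and up to 3.0 x ULN (Grade 2) the action is "Recommendation: Interrupt study treatment". Dosing resumes at the same level if the value settles within 7 days, and one level lower otherwise. The next row, "Grade 3 (> 3.0 - 10.0 × ULN", also recommends interruption. The top row, "Grade 4 (> 10.0 × ULN", is a mandatory permanent stop. Both of these rows carry an asterisk. The footnote begins "If total bilirubin > 3.0 × ULN is due to the indirect (non-conjugated) component only" and, once hemolysis has been excluded, ends "then reduce 1 dose level and continue treatment at the discretion of the Investigator".

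**Bilirubin, Table 10-3 (Protocol 10.5, Appendix 5).** The column of required actions reads:

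- > 1.5-3.0 x ULN: "Maintain treatment Repeat LFTs within 48-72 hours"
- > 3-10 x ULN, without known Gilbert syndrome: "Interrupt treatment Repeat LFT within 48-72 hours Hospitalize if clinically appropriate"
- > 10 x ULN: "Discontinue the study treatment immediately Hospitalize the participant"

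**ALT.** With a normal baseline, Table 6-3 recommends interruption at Grade 2 (above 3 and up to 5 x ULN). Table 10-2 leaves dosing unchanged above 3 x ULN when bilirubin is normal and there are no symptoms.

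**Skeletal muscle Grade 4 (lesser point).** Table 6-3 sets a mandatory permanent stop. It then allows a restart in some cases, after discussion with the Medical Monitor and a rheumatology consultation, and names no recovery grade. The Grade 2-3 row requires recovery to Grade 1 or better.

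**The concern.** A site with an isolated bilirubin of, say, 2 x ULN finds one instruction to hold the drug in Section 6.5.1 and one to keep giving it in Section 10.5. Footnote 4 to the assessment schedule in Section 1.3 sends sites to both places for toxicity testing. Section 2.3 recommends monitoring for hepatic effects on the basis of the toxicology findings.

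What is at stake is consistent safety conduct. Two sites could treat the same value differently, and a participant could lose doses or a dose level at one site and not at the other. The SAP summarizes dose interruptions and reductions (Section 2.5.1) and adverse events leading to dose adjustment (Section 2.9.1.2), so uneven handling would also show in those descriptive tables.

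**Working it through.** The plan gives no figure to reproduce, so the check sets the rows side by side.

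| Isolated finding | Table 6-3, main row | Footnote * (indirect only, no hemolysis) | Appendix 5 | Result |
|---|---|---|---|---|
| Bilirubin > 1.5-3.0 x ULN | Interrupt (recommended) | Not applicable | Maintain (Table 10-3) | Differ for every participant |
| Bilirubin > 3-10 x ULN | Interrupt (recommended) | May continue 1 level lower | Interrupt, if no known Gilbert syndrome (Table 10-3) | Main rows agree; differ only through the footnote |
| Bilirubin > 10 x ULN | Permanent stop (mandatory) | May continue 1 level lower | Stop at once and hospitalize (Table 10-3) | Main rows agree; differ only through the footnote |
| ALT > 3-5 x ULN, normal baseline and bilirubin, no symptoms | Interrupt (recommended) | Not applicable | No change (Table 10-2) | Differ |

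**Count.** The main bilirubin rows differ in 1 of 3 ranges and agree in 2 of 3. In those 2 a conditional difference remains. At > 3-10 x ULN it is narrowed further to participants without known Gilbert syndrome.

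**How close the first range is.** Inclusion criterion 9 allows total bilirubin up to 1.5 x ULN. From that cap, 1.5/1.5 = 1.0, so any rise enters the range. From 1.0 x ULN, a rise of more than 1.5-fold is needed.

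**Does any range force a breach?** Section 6.5.1 forbids deviation from mandatory interruptions and reductions only.

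- At > 1.5-3.0 x ULN, maintaining departs from a recommendation only. Interrupting fits Section 10.5's own text, which lets the site consider interruption once the rise is confirmed.
- At > 3-10 x ULN, a site that interrupts satisfies both tables.
- At > 10 x ULN, a site that discontinues and hospitalizes satisfies both tables, because the footnote permits continuing and does not require it.

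**Is there a precedence rule?**

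- Section 1.3 says interruptions for toxicity follow the Section 6.5 criteria. Section 6.1.3 points to Section 6.5 for dose modification. Section 6.5.1 places the dose modifications in Tables 6-3 and 6-4.
- Section 10.5 takes its liver events from Table 6-3, but it also requires a standardized process to be followed and names Tables 10-1 and 10-2 for actions.
- The one tie-break, the conservative-action text under Table 6-3, covers combined ALT/AST and bilirubin elevations below the combined thresholds. It does not cover disagreement between tables.

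**Within Table 6-3.** The asterisk on the Grade 4 bilirubin row attaches a discretionary continuation to a mandatory stop.

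**The case against.** The strongest reply is that the protocol already shows where dosing rules live. Three sections point to Section 6.5, and Table 10-3 is titled as follow-up. The note closing the bilirubin block of Table 6-3 says that an isolated rise is not typical of drug-induced liver injury and asks that other causes be excluded before dosing is changed on bilirubin alone. Section 10.5 likewise asks for confirmation before interruption is considered. On this reading, interruption depends on work-up in both places.

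Much of this stands. It makes Table 6-3 the likelier authority and softens the > 1.5-3.0 x ULN mismatch. It does not remove it: Table 10-3 still prints a dosing action under required actions, the opposite of the one in Table 6-3, and no sentence settles the matter.

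A reader might infer that the tables conflict outright in all three bilirubin ranges. They do not; above 3 x ULN the ordinary case is handled alike. A reader might also infer that above 10 x ULN a site cannot follow both tables. It can, by discontinuing and hospitalizing. Nor is the skeletal muscle Grade 4 cell a waiver of the mandatory stop. It reads as a default stop with a gated exception, and Section 6.5.1 largely supplies a lower restart dose. Only the recovery grade is missing.

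**Conclusion.** The point holds in limited form and should be corrected, at the lower end of that category. There are two outright mismatches (bilirubin > 1.5-3.0 x ULN and asymptomatic ALT > 3-5 x ULN), both against Table 6-3 recommendations. There are two conditional mismatches through footnote *, one of them attached to a row that is otherwise a mandatory stop. Precedence is implied but not stated.

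The consequence is uneven handling of the same liver value across sites. The ORR definition, test and sample size do not depend on it.

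The documents give no event rates, so the number of participants affected cannot be estimated; values above 10 x ULN and Grade 4 muscle toxicity are probably rare. The conclusion assumes that Table 6-3 is meant to govern dosing, as the cross-references suggest. The sponsor should confirm that.

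**What to change.** 1. Section 10.5: add one sentence saying that Table 6-3 governs dosing and that the Appendix 5 tables govern follow-up.
2. Table 10-3, > 1.5-3.0 x ULN: replace the maintain action with the Table 6-3 Grade 2 action.
3. Table 10-2, ALT > 3 x ULN with normal baseline and no symptoms: replace the no-change action with the Table 6-3 Grade 2 action. Check the neighbouring > 5 x ULN row as well. It interrupts only after more than two weeks, while Table 6-3 recommends interrupting at Grade 3 without that delay.
4. Table 10-3, > 3-10 x ULN only: add the footnote * exception.
5. Table 6-3, Grade 4 bilirubin: remove the asterisk and cap the footnote at 10 x ULN, so that a value above 10 x ULN means permanent discontinuation in both tables. Writing continued dosing above 10 x ULN into Table 10-3 would also reconcile the tables, but in the less safe direction.
6. Minor: keep the default permanent stop for skeletal muscle Grade 4 and add recovery to Grade 1 or better as a condition of the existing restart exception.

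The cost is a few table cells and one sentence. It needs a protocol amendment and can travel with the next one. Data collection and analysis do not change.

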6.5.2 Definitions of dose limiting toxicities (DLTs)

Not Applicable

6.5.3 Follow-up for toxicities

Participants whose treatment is interrupted or permanently discontinued due to an adverse event or clinically significant laboratory value must be followed up at least once a week (or more frequently if required by institutional practices, or if clinically indicated) for 4 weeks, and subsequently at approximately 4-week intervals, until resolution or stabilization of the event, whichever comes first. Appropriate clinical experts such as ophthalmologists, endocrinologists, dermatologists, psychiatrists, neurologists etc., should be consulted as deemed necessary. All participants must be followed up for adverse events and serious adverse events for 30 days following the last doses of study treatment.

Table 6-5 outlines the follow-up evaluation recommended for toxicities of specific types and CTCAE grades.

^{**}Dose reduction below 100 mg once a day is not allowed.

Page 67 of 164

Table 0-0 Tollow-up evaluations for Selected toxicities	
TOXICITY	FOLLOW-UP EVALUATION
Blood and lymphatic system disorders	Test once a week until ≤ CTCAE grade 1, then restart treatment. Continue to test weekly until resolution to baseline or stabilization.
Investigations (hematologic) Neutropenia ≥ CTCAE grade 3 Thrombocytopenia ≥ CTCAE grade 3	Test once a week until ≤ CTCAE grade 1, then restart treatment. Continue to test weekly until resolution to baseline or stabilization. Perform physical exam for check on bruising in case of major thrombocytopenia.
Investigations (metabolic) Amylase or lipase ≥ CTCAE grade 3	Test once a week until ≤ CTCAE grade 2, then restart treatment. Continue to test weekly until resolution to ≤ CTCAE grade 1 or stabilization. A CT scan or equivalent imaging procedure to assess the pancreas, liver, and gallbladder is recommended within 7 days of the first occurrence of any ≥ CTCAE grade 3 result, to exclude disease progression or potential other liver disease. In participants with serum triglycerides ≥ 500 mg/dL, urine amylase also needs to be tested.
Cardiac disorders QT and ECG ECG changes indicative of ischemic event	Twice weekly ECGs until normalization or stabilization of ECG findings then restart treatment.

Follow up on potential drug-induced liver injury (DILI) cases 6.5.3.1

Transaminase increase combined with total bilirubin increase may be indicative of potentially severe DILI. These cases should be considered as clinically important events and assessed appropriately to establish the correct diagnosis. The required clinical information, as detailed below, should be sought to obtain the medical diagnosis of the most likely cause of the observed laboratory abnormalities.

The threshold for potential DILI may depend on the participant's baseline AST/ALT and total bilirubin value; participants meeting any of the following criteria will require further follow-up as outlined below:

- For participants with normal ALT and AST and total bilirubin value at baseline: AST or ALT $> 3.0 \times ULN$ combined with total bilirubin $> 2.0 \times ULN$
- For participants with elevated AST or ALT or total bilirubin value at baseline: [AST or ALT >3.0 × baseline] OR [ALT or AST > $8.0 \times ULN$], whichever occurs first, combined with [total bilirubin $> 2.0 \times$ baseline AND $> 2.0 \times$ ULN]

As DILI is essentially a diagnosis of exclusion, other causes of abnormal liver tests should be considered and their role clarified before DILI is assumed to be the cause of liver injury.

A detailed history, including relevant information such as review of ethanol consumption, concomitant medications, herbal remedies, supplement consumption, history of any preexisting liver conditions or risk factors, should be collected.

Laboratory tests should include ALT, AST, total bilirubin, direct and indirect bilirubin, Gamma-glutamyl transferase (GGT), prothrombin time (PT)/ International Normalized Ratio (INR), alkaline phosphatase, albumin, and creatine kinase. If available, testing of Glutamate Dehydrogenase (GLDH) is additionally recommended.

Evaluate status of liver metastasis (new or exacerbation) or vascular occlusion – e.g. using CT, Magnetic Resonance Imaging (MRI), or duplex sonography.

Perform relevant examinations (Ultrasound or MRI, Endoscopic retrograde cholangiopancreatography (ERCP)) as appropriate, to rule out an extrahepatic cause of cholestasis. Cholestasis (is defined as an ALP elevation > 2.0 × ULN with R value < 2 in participants without bone metastasis, or elevation of the liver-specific ALP isoenzyme in participants with bone metastasis).

Note: The R value is calculated by dividing the ALT by the ALP, using multiples of the ULN for both values. It denotes whether the relative pattern of ALT and/or ALP elevation is due to cholestatic ($R \le 2$), hepatocellular ($R \ge 5$), or mixed ($R \ge 2$ and $R \ge 1$) liver injury. In clinical situations where it is suspected that ALP elevations are from an extrahepatic source, the GGT can be used if available. GGT may be less specific than ALP as a marker of cholestatic injury, since GGT can also be elevated by enzyme induction or by ethanol consumption. It is more sensitive than ALP for detecting bile duct injury.

Table 6-6 provides guidance on specific clinical and diagnostic assessments which can be performed to rule out possible alternative causes of observed LFT abnormalities.

If required, these laboratory tests will be performed at the local laboratory.

Table 6-6 Guidance on specific clinical and diagnostic assessments

	 
Disease	Assessment
Hepatitis A, B, C, E	IgM anti-HAV; HBsAg, IgM & IgG anti-HBc, HBV DNA; anti-HCV, HCV RNA, IgM & IgG anti-HEV, HEV RNA
CMV, HSV, EBV infection	IgM & IgG anti-CMV, IgM & IgG anti-HSV; IgM & IgG anti-EBV
Autoimmune hepatitis	Antinuclear Antibodies (ANA) & Anti-Smooth Muscle Antibody (ASMA) titers, total IgM, IgG, IgE, IgA
Alcoholic hepatitis	Ethanol history, GGT, MCV, CD-transferrin
Nonalcoholic steatohepatitis	Ultrasound or MRI
Hypoxic/ischemic hepatopathy	Medical history: acute or chronic congestive heart failure, hypotension, hypoxia, hepatic venous occlusion. Ultrasound or MRI.
Biliary tract disease	Ultrasound or MRI, ERCP as appropriate.
Wilson disease (if <40 years old)	Caeruloplasmin
Hemochromatosis	Ferritin, transferrin
Alpha-1-antitrypsin deficiency	Alpha-1-antitrypsin

Other causes should also be considered based upon participants' medical history (hyperthyroidism / thyrotoxic hepatitis – T3, T4, TSH; cardiovascular disease / ischemic hepatitis – ECG, prior hypotensive episodes; Type 1 diabetes mellitus / glycogenic hepatitis). If required, these laboratory tests will be performed at the local laboratory.

Obtain PK sample to determine exposure to study treatment and metabolites.

Following appropriate causality assessments, as outlined above, the causality of the treatment is estimated as "probable" (i.e., > 50% likely), if it appears greater than all other possible causes of liver injury combined. The term "treatment-induced" indicates probably caused by the treatment, not by something else, and only such a case can be considered a DILI case and should be reported as an SAE.

All cases confirmed on repeat testing meeting the laboratory criteria defined above, with no other alternative cause for LFT abnormalities identified, should be considered as "medically significant," and thus, meet the definition of SAE and should be reported as a SAE using the term "potential treatment-induced liver injury." All events should be followed up with the outcome clearly documented.

